 - o from randomization to the first day of achieving sustained (i.e., at least 2 days) resolution of fever for subjects who presented with fever at any point between enrollment and day 2 post randomization

- with temperature <38C or >=38C experienced in total during the first 28 days post randomization
- o from randomization to the first day post randomization of achieving oxygenation of SpO2>=96% in room air when resting for subjects who presented with SpO2>93% and <96% in room air, when resting, at enrollment
- o with oxygenation of SpO2>= 96% or SpO2>93% in room air, when resting, in total during the first 28 days post randomization

3. COVID-19 related deterioration and mortality

- **3a. Deterioration and mortality rates:** Proportion of treatment group, versus placebo group, respectively, who per subject reporting or medical records by day 14, day 28 and by day 60 post randomization had experienced:
 - o an emergency department visit, other than at study enrollment or study visits
 - hospitalization for COVID-19
 - o hospitalization for COVID-19 requiring oxygen
 - hospitalization for COVID-19 requiring ICU
 - o hospitalization for COVID-19 requiring ventilation
 - o COVID-19 related death
 - death
 - hospitalization or death
- **3b.** *Time to and length of deterioration*: Comparison of treatment group versus placebo group, respectively, in the number of days
 - o from randomization until the first day of experiencing hospitalization for COVID-19
 - o of hospitalization for COVID-19 experienced in total by day 14, by day 28 and by day 60 post randomization
 - o of hospitalization for COVID-19 requiring oxygen experienced in total by day 14, by day 28 and by day 60 post randomization
 - of hospitalization for COVID-19 requiring ICU experienced in total by day 14, by day 28 and by day 60 post randomization
 - o of hospitalization for COVID-19 requiring ventilation experienced in total by day 14, by day 28 and by day 60 post randomization

4. WHO 9-Point Ordinal Scale

- 0. Uninfected or "no clinical or virological evidence of infection"
 - a. defined as subject answering "Yes" to "In the past 24 hours, have you returned to your usual health (before your COVID-19 illness)?"
- 1. Not hospitalized, no limitations on activities
 - a. defined as subject answering "Yes" to "In the past 24 hours, have you returned to your usual activities (before your COVID-19 illness)?"
- 2. Not hospitalized, limitation on activities

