 - a. defined as subject answering "No" to "In the past 24 hours, have you returned to your usual activities (before your COVID-19 illness)?"
- 3. Hospitalized, not requiring supplemental oxygen
- 4. Hospitalized, requiring supplemental oxygen
- 5. Hospitalized, on non-invasive ventilation or high flow oxygen devices
- 6. Hospitalized, intubated
- 7. Hospitalized, advanced life support including invasive mechanical ventilation or ECMO
- 8. Death
- **4a)** Ordinal scale rates: proportion of treatment group versus placebo group, respectively who had experienced:
 - o an improvement from scale 2 at randomization to scale 1 or 0 on days 4, 7, 10, 14, 21, 28, 42, 60 post randomization,
 - o an improvement from scale 1 at randomization to scale 0 on days 4, 7, 10, 14, 21, 28, 42, 60 post randomization
 - o a sustainment from scale 1 at randomization to scale 1 on days 4, 7, 10, 14, 21, 28, 42, 60 post randomization
 - o any improvement of the scale (i.e., at least a 1-point decrease) between enrollment and days 7, 14, 28, 42, 60 post randomization
 - any worsening of the scale (i.e., at least a 1-point increase) between enrollment and days 7,
 14, 28, 42, 60 post randomization
 - o scale 4 or higher by day 28 or day 60 post randomization
 - o scale 6 or higher by day 28 or day 60 post randomization

- *4b) Ordinal scale averages, highs, and lows:* Comparison of treatment group versus placebo group, respectively, at days 14, 28 and 60 post randomization in the
 - o average of daily scale value on that day
 - o overall average of daily scale value experienced since enrollment
 - o in the worst (i.e., highest) daily scale value experienced since enrollment
 - o in the best (i.e., lowest) daily scale value experienced since enrollment
- **4c)** Time to improvement: Comparison of treatment group versus placebo group, respectively, in the number of days from enrollment until first experiencing a 1-point improvement sustained over at least 2 days by day 14, day 28 and by day 60 post randomization
- *4d) Length of ordinal scale experience:* Comparison of treatment group versus placebo group, respectively, in the total number of days by day 14, day 28 and by day 60 post randomization on which subjects experienced a given scale value (i.e., 3, 4, 5, 6, 7)

5. Surrogate markers of COVID-19-related inflammation and organ involvement

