Subjects may withdraw voluntarily from participation in the study at any time and for any reason. Subjects may also be withdrawn on the basis of the Investigator's clinical judgment. This study may be terminated at the discretion of MedStar Health or of any regulatory agency for reasons including safety and/or treatment effect.

For enrolled subjects we anticipate that the main reasons for discontinuation of therapy will be either withdrawal of consent for continuation in the study or inability to tolerate the study. Other instances may include patient death, inability to take the study drug from severity of illness or inhospital complexity of illness. Subjective intolerance of the drug from minor side effects or alternatively cessation of COVID-19 related symptoms well ahead of the 28-day schedule may cause patients to want to discontinue the drug. With regards to drug toxicity itself, we anticipate minor symptomatology from adverse effects, such as headache, dizziness, nausea and vomiting, abdominal discomfort and rash (see also 1.4) based on prior human trial experience with the study drug. Should any subject dosed on the study drug experience seizures, which was reported as an

unrelated adverse event in an epilepsy trial, that individual would be subject to discontinuation out of an abundance of caution. Any emergent symptom that has no clear cause will result in a hold on subsequent study drug dosing until protocol assessment by the Study Investigator. The reasons for discontinuation of study drug will be documented clearly. In all cases study protocol monitoring will continue for the entire 60 days of the protocol as long as the subject stays consented.

When a subject withdraws or is withdrawn before completing the study, the date and reason for withdrawal are to be documented. Subjects who withdraw or who are withdrawn prematurely are to attend an early termination, at which time they will complete all assessments as outlined in the Schedule of Events (Table 1); moreover they will be encouraged to stay enrolled so that further safety and outcome information can be collected and analyzed.

In the event that a subject is withdrawn prematurely due to an adverse event or serious adverse event, the adverse event or serious adverse event will be followed until it resolves or stabilizes, or until it is judged by the Investigator to be no longer clinically significant.

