8.4 Safety & Tolerability Analyses

All safety & tolerability analyses will be performed on the Safety Population. The safety data will be presented in individual listings and summary tables.

Overall safety will be assessed by the number of belnacasan VX-765/RVT-201/MSR-001 dosed subjects experiencing a grade 4 or 5 SAE during the trial. Of 20 subjects enrolled in the belnacasan group, 3 or more developing a grade 4 or 5 SAE probably related to belnacasan would be

considered unlikely due to chance. Therefore, belnacasan will be determined safe if no more than

2 subjects develop a grade 4 or 5 SAE in the belnacasan group probably related to belnacasan.

In terms of stopping rules, should two or more subjects develop a similar Grade 3 SAE that is at

least possibly related to belnacasan or should one or more subjects develop a \geq Grade 4 SAE that

is at least possibly related to belnacasan, the trial will be paused for DSMB safety review.

Primary Endpoint Analysis

Primary endpoints of adverse and serious adverse events (AE/SAE) will be assessed by Poisson

regression for count data. Events will be counted out to 60 days from randomization to belnacasan

or placebo groups. Because some subjects may be followed for less than 60 days, subject follow-

up time will be included in the Poisson regression as the exposure time variable. If counts are not

Poisson-distributed, either over- or under-dispersed, negative binomial regression will be to

analyze AE/SAE events with appropriate adjustment for over/under dispersion. Comparison of

belnacasan vs. placebo will be expressed as the incidence rate ratio (IRR).

Adverse Events

AEs will be coded according to the latest version of the Medical Dictionary for Regulatory

Activities (MedDRA). The intensity/severity of AEs will be graded according to NCI-CTCAE (see

Section 7.3).

TEAEs, AEs leading to study treatment discontinuation, AEs leading to dose interruption, AEs

related to study medication, SAEs, and AEs leading to death will be summarized by system organ

class, preferred term, and study period. A summary of AEs that are CTCAE Grade 3 or higher, as

well as the most frequent preferred terms, will be provided.

If a subject experiences the same adverse events multiple times within a period, then the event will

be counted only once within the period and by greatest severity.

Descriptive statistics will be used to summarize the safety data.

Clinical Laboratory Values

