8.5 Treatment Effect Analyses

Secondary Endpoint Analyses

Event counts over 60 days will be analyzed by Poisson regression as described above in 8.4. Time

to events will be analyzed by Cox regression. Differences between belnacasan and placebo with

respect to change in continuous endpoints will be assessed by mixed effects models for continuous

repeated measures data and mixed effects logistic models for repeated categorical variables.

Endpoint proportions of belnacasan and placebo groups will be assessed by contingency table

analysis (chi-square).

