8.6 Handling of Missing Data

Although every effort will be made to obtain complete data, missing values will likely occur when

data are collected longitudinally. Patterns of missingness over time as well missingness with

MOD00008997 IRB Approved 12/23/2021 - 11/9/2022

Version 2.2 12/14/21 Page 51 of 66

respect to demographic and clinical variables will be assessed. For Poisson and Cox regression analyses, all data can be used up to subject dropout time.

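### The cumulative day-14, day-28 and day-60 proportions go to a chi-square table that cannot use partial follow-up, and no rule says how subjects lost early are counted

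*Combined protocol and SAP*

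**What the plan says.** Section 3.4 defines two kinds of proportion endpoint.

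- **Cumulative.** Endpoint 3a (emergency visit, hospitalization and its levels, death) is the proportion of each group "who per subject reporting or medical records by day 14, day 28 and by day 60 post randomization had experienced" the event. The last two items of 4a have the same form, for example "scale 4 or higher by day 28 or day 60 post randomization".
- **Status on fixed days.** Recovery endpoints 1a and 1b are read on days 4, 7, 10, 14, 21, 28, 42 and 60.

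Section 8.5 states "Endpoint proportions of belnacasan and placebo groups will be assessed by contingency table" analysis (chi-square). It also plans mixed effects models for continuous "repeated measures data and mixed effects logistic models for repeated categorical variables". It does not say which proportions go to which method, and it gives no denominator.

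On incomplete follow-up, 8.4 says "Because some subjects may be followed for less than 60 days" and adds exposure time to the Poisson model. Section 8.6 expects that "missing values will likely occur when" data are gathered over time, and its only rule on use is "For Poisson and Cox regression analyses, all data can be used up to subject dropout time". The chi-square proportions are not mentioned.

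Section 8.1 analyses everyone who took at least one dose and keeps subjects who stop the drug in follow-up while they remain consented. Section 5.3 expects the main reasons for stopping therapy to be "withdrawal of consent for continuation in the study or inability to tolerate the study". It also names early cessation of symptoms as a reason for wanting to stop.

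**The concern.** A two-by-two table of events by day 60 needs each subject classified as event or no event through day 60. A subject who withdraws consent on day 5 without an event cannot be classified from the data. The plan allows for short follow-up in the Poisson and Cox analyses but not in the table.

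Three countings are open to the analyst: keep dropouts in the denominator as event-free, drop them all, or keep only those who already had the event. They can give different answers from the same data, and two of them are biased in opposite directions when dropout is unequal. The secondary objective is an effect size, and 8.7 says it will inform a larger trial, so the harm is an estimate that depends partly on dropout and on an unwritten rule.

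**Working it through.** **Inputs from the documents.** 20 subjects per arm and a 5% alpha (8.7); chi-square test (8.5); horizons of days 14, 28 and 60 (3.4). The documents give no dropout rate and no event risk. They contain no figure for these endpoints to reproduce.

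**Assumptions.** Day-28 horizon; exponential event times; dropout uniform over days 1 to 28 and independent of outcome; two-sided uncorrected chi-square.

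**Formulas.** Let p be the true risk by day 28, d the dropout fraction, and λ = −ln(1 − p)/28. The chance that a dropout has the event before leaving is q = 1 − [exp(−λ) − exp(−28λ)]/(27λ).

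- Dropouts kept, counted as no event: (1 − d)p + dq = p − d(p − q).
- Dropouts kept only if they had the event: [p − d(p − q)]/[1 − d(1 − q)].
- All dropouts excluded: p under independent dropout, with fewer subjects.
- Censored at last contact (Kaplan-Meier): targets p under independent dropout.

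**Cumulative harm endpoints (3a, 4a), no true effect, p = 15%.** Here q = 8.0% and p − q = 7.0 points.

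| Dropout, belnacasan v placebo | Counted as no event | Difference | Kept only if event | Difference |
|---|---|---|---|---|
| 20% v 5% | 13.6% v 14.6% | −1.1 | 16.7% v 15.4% | +1.3 |
| 30% v 5% | 12.9% v 14.6% | −1.8 | 17.8% v 15.4% | +2.4 |

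The first difference follows from (0.20 − 0.05) × 7.0 = 1.05 points and the second from (0.30 − 0.05) × 7.0 = 1.76. The sign reverses with the counting rule. Under the first rule the chi-square test still rejects about 5% of the time (4.9% and 5.1% by exact enumeration), so the harm is to the estimate rather than the test.

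A harsher case puts all dropout before any event. At p = 10% and dropout of 30% v 5%, the table shows 0.70 × 10 = 7.0% v 0.95 × 10 = 9.5%, a ratio of 0.74, with 3.7% rejection.

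**Recovery endpoints, only if 1a and 1b are tabulated as first achievement by day 28 with dropouts counted as not recovered.**

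| True recovery | Dropout | Observed | True difference | Observed difference | Chi-square rejection |
|---|---|---|---|---|---|
| 90% v 50% | none | 90% v 50% | 40 | 40 | 84% |
| 90% v 50% | 20% v 5% | 84.6% v 48.9% | 40 | 36 | 70% |
| 90% v 50% | 30% v 10% | 81.9% v 47.9% | 40 | 34 | 64% |
| 70% v 70% | 20% v 5% | 64.7% v 68.7% | 0 | −4 | 6% |

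For the last row, p − q = 26.7 points and 0.15 × 26.7 = 4.0. Simulation of the same cases agrees within 2 points of power, and Kaplan-Meier returned differences of about 40 and 0 points.

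**Excluding all dropouts.** With independent dropout there is no spurious effect: with 14 v 19 subjects left, false positives are 5.3% at p = 80% and 3.3% at p = 10%. The cost is lost information: in the 90% v 50% case with 20% v 5% dropout, power is 77% rather than 84%.

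**The case against.** The strongest reply is that the plan never says dropouts count as event-free or as not recovered. A reader might infer this, because the endpoints are worded as proportions of each group and 8.1 includes all dosed subjects. But it remains an inference. Where 8.4 does state denominators (laboratory values, EKG, physical examination), it uses subjects with data; those rules cover safety summaries only, but they make exclusion a fair alternative reading.

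Four further points stand.

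- A reader might infer that short follow-up is certain. Section 8.4 says only that it may occur.
- Stopping the drug does not end follow-up. Sections 5.3, 7.2 and 8.1 continue it while consent lasts, and 3a also draws on medical records. Intolerance alone therefore does not create missing outcomes.
- It is tempting to apply the larger recovery figures to the cumulative endpoints. The documents do not support this: 1a and 1b are status on fixed days, time to recovery (1c) and to hospitalization (3b) already go to Cox regression, and the mixed logistic model can take repeated status.
- These are secondary endpoints in a trial described as hypothesis generating. At 15% risk, the 95% half-width for a difference is 1.96 × √(2 × 0.15 × 0.85/20) = 22 points, far more than a 1 to 2 point shift.

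Exclusion does not fully rescue the table, however. It discards observed follow-up, and it is biased if withdrawal is related to outcome, which 5.3 makes plausible by naming early symptom resolution as a reason to stop treatment. Informative dropout would bias Kaplan-Meier too; its good result above depends on the independence built into the calculation.

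**Conclusion.** The concern holds for 3a and the two cumulative items of 4a. Their stated analysis cannot use partial follow-up, and no rule covers subjects lost early. The direction of any bias depends on that missing rule. Under the literal whole-group reading it favours the arm with more dropout by about 1 to 2 points, assuming 15% risk and 20% to 30% v 5% dropout. The 4 to 6 point shift for recovery arises only if 1a and 1b are tabulated as first achievement and dropouts are counted as not recovered. All these sizes rest on dropout rates and risks that the documents do not give.

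The documents do not support saying that the plan codes dropouts as event-free, that unequal dropout will occur, or that a false drug effect will follow. A change is still worth making, because a better method costs little and the output is meant to guide the next trial.

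**What to change.** 1. **Section 8.5, endpoint 3a and the cumulative items of 4a:** report the cumulative incidence in each arm, censored at last contact, at days 14, 28 and 60 for 3a and at days 28 and 60 for 4a. Give the arm difference with its 95% interval and the crude n/N beside it. Use Kaplan-Meier, or Aalen-Johansen where death competes (for example, hospitalization). The 4a items include death as scale value 8, so Kaplan-Meier suffices there.
2. **Section 8.5, endpoints 1a and 1b:** name the mixed effects logistic model already planned as the analysis of status on the fixed days, using all available data. First achievement stays with 1c.
3. **Section 8.6:** extend the rule on partial data to these endpoints. Add a sensitivity analysis for informative dropout, for example with dropouts counted once as events and once as non-events.
4. **Table 1 and 7.2:** reconcile them. Table 1 ends daily tracking at day 28 or early termination, while 7.2 asks subjects who stop the drug to continue the diary. This decides how much symptom data will be missing.

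The cost is SAP wording and modest programming; times for 1c and 3b are already derived, but event dates for the other 3a and 4a items must be available. The intervals are approximate at 20 per arm, and the main estimate assumes non-informative censoring, as the Cox and Poisson models do.

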8.6 Handling of Missing Data

Although every effort will be made to obtain complete data, missing values will likely occur when

data are collected longitudinally. Patterns of missingness over time as well missingness with

MOD00008997 IRB Approved 12/23/2021 - 11/9/2022

Version 2.2 12/14/21 Page 51 of 66

respect to demographic and clinical variables will be assessed. For Poisson and Cox regression analyses, all data can be used up to subject dropout time.

8.7 Sample Size Considerations

A total of 40 subjects will be randomized, 20 to belnacasan (VX-765/RVT-201/MSR-001) 900 mg TID and 20 to placebo. As this is a proof-of-concept study, it will likely not be powered to detect belnacasan – placebo differences that are clinically meaningful. For example, the observed difference in endpoint rate ratios would need to be over 60% to achieve 80% power with an alpha error rate of 5% for 20 subjects in each group. This study will provide an estimate of the belnacasan effect size to inform a larger trial where a more clinically meaningful difference can be detected.

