Statistical **Study Populations: Considerations** • Safety & Tolerability Population: All enrolled subjects who have received at least 1 dose of IP (belnacasan or placebo) will be studied. Even if subjects have discontinued study treatment, as long as they maintain consent, they will continue to be in the study and included in analysis, i.e., their safety and tolerability information will continue to be collected for at least 60 days. • Treatment Effect Evaluable Populations: All enrolled subjects who have received at least 1 dose of IP (belnacasan or placebo) will be studied. Even if subjects have discontinued study treatment, as long as they maintain consent, they will continue to be in the study and included in analysis, i.e., their outcome information will continue to be collected for at least 60 days. **Analysis Methods:** FDA Data Standard Guidelines will be followed. Continuous variables will be summarized using the number of observations, number of observations above the limit of quantification (if applicable), mean, standard deviation (SD) median, and range. Categorical variables will be summarized using frequency counts and percentages. Comparison of belnacasan and placebo groups will utilize Poisson regression for counts, Cox proportional hazards regression for time-to-event data and mixed effects models for continuous and categorical data obtained over study days. **Primary Safety and Tolerability Analysis:** All safety & tolerability analyses will be performed on the Safety Population. The safety data will be presented in individual listings and summary tables. Overall safety will be assessed by the number of belnacasan dosed subjects experiencing a grade 4 or 5 SAE during the trial. Of 20 subjects enrolled in the belnacasan group, 3 or more developing grade 4 or 5 SAE probably related to belnacasan would be considered unlikely due to chance. Therefore, belnacasan will be determined safe if no more than 2 subjects develop a grade 4 or 5 SAE in the belnacasan group probably related to belnacasan. In terms of stopping rules, should two or more subjects develop a similar Grade 3 SAE that is at least possibly related to belnacasan or should one or more subjects develop a \geq Grade 4 SAE that is at least possibly related to belnacasan, the trial will be paused for DSMB safety review. **Secondary Treatment Effect Endpoint Analysis:** Event counts over 60 days will be analyzed by Poisson regression. Time to events will be analyzed by Cox regression. Differences between belnacasan and placebo with respect to change in continuous endpoints will be assessed by mixed effects models for continuous repeated measures data and mixed effects logistic models for repeated categorical variables. Endpoint proportions of belnacasan and placebo groups will be assessed by contingency table analysis (chi-square). **Sample Size Considerations:** As this is a proof-of-concept study, it will likely not be powered to detect belnacasan - placebo differences that are clinically meaningful. For example, the observed difference in endpoint rate ratios would need to be over 60% to achieve 80% power with an alpha error rate of 5% for 20 subjects in each group. This study will provide an estimate of the belnacasan effect size to inform a larger trial where a more clinically meaningful difference can be detected. **Initial Date** November 2021 **Completion Date** April 2022

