All data collected by the Study Team and recorded by the subjects will be entered into the EDC per the schedule of events. OnCore, a Clinical Trial Management System in which subject visits

MOD00008997 IRB Approved 12/23/2021 - 11/9/2022

can be monitored as well as Case Report Forms developed, will be used for this trial. Subjects will be asked to hand in their subject diary during visits on days 7, 14, 21, and 28.

Background Standard of Care

All eligible subjects will receive background standard of care, however there are certain prohibited medications subjects cannot be given while dosed with the IP as outlined in Section 5.4. Background standard of care will be commensurate with disease severity and aligned to standards at the time of the trial. At present, standard of care includes vaccines, antiviral treatment with remdesivir, monoclonal antibodies against SARS-CoV-2, dexamethasone, supplemental oxygen, noninvasive and invasive ventilation, antibiotics, vasopressors, anti-coagulation and ECMO; but this may evolve over the coming months as new therapies or treatments come online including offlabel use of other drugs.

Patients recruited to the study will not be asked to forgo background standard of care in any way. Recruitment will be based on inclusion and exclusion criteria and include individuals evaluated for suspected COVID-19 in a MedStar Urgent care or the Emergency Room setting, and triaged not to need in-hospital care. These individuals have the potential but not the likelihood for hospital admission with worsening COVID-19 disease progression. Current outpatient standard of care includes symptomatic treatment and this will not be altered to the point that analgesics and antipyretics will be held. Patients whose COVID-19 related illness deteriorates to the point that they need ambulatory medical care or hospitalization will remain in the study and medical care as determined by managing physicians will not be subverted in any manner as part of the study. Patient data collection as per study diary and study visits will be maintained for the minimum 60 days and study drug will be provided and monitored for compliance unless there is an indication for discontinuation of study drug, see section on drug discontinuation.

Study Population

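### Section 8.7 ties 80% power to an observed rather than a true effect, and sections 8.4 and 8.5 name no test, interval or zero-event rule for sparse counts such as SAEs

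*Combined protocol and SAP*

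**What the plan says.** **Power.** Section 8.7 randomizes 40 subjects, 20 per arm, and says "the observed difference in endpoint rate ratios would need to be over 60% to achieve 80% power" at an alpha of 5%. The Synopsis repeats this. It is the only power figure in the document. No endpoint, placebo rate, direction or sidedness goes with it. The sentence is offered as an example, and the one before it concedes the main limitation: "As this is a proof-of-concept study, it will likely not be powered to detect" differences of clinical interest.

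**Counts.** Section 8.4 states: "Primary endpoints of adverse and serious adverse events (AE/SAE) will be assessed by Poisson" regression, with follow-up time as exposure, a negative binomial fallback for over- or under-dispersion, and the incidence rate ratio (IRR) as the effect measure. Section 8.5 extends this to secondary endpoints: "Event counts over 60 days will be analyzed by Poisson regression as described above in 8.4". Neither section names a Wald, score, likelihood-ratio or exact test, an interval method, or what to report when an arm has no event.

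**Proportions.** Section 8.5 does name a test here: "Endpoint proportions of belnacasan and placebo groups will be assessed by contingency table" analysis, by chi-square.

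**Expected rarity.** No SAE or hospitalization rate is given. Section 7.9 makes hospitalization an SAE criterion, and section 5.1 says of the recruited patients: "These individuals have the potential but not the likelihood for hospital admission with worsening COVID-19 disease progression".

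**The concern.** Two things stand out.

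First, power is the chance of a significant result given an assumed true effect. Tied to an observed difference, the sentence invites a reader to treat 60% as the bar that the results must clear. The trial's declared product is an effect size for a larger trial, so dismissing an observed 45% or 50% reduction on that ground would misuse the data. With no event rate stated, the reader also cannot tell which endpoints the figure covers.

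Second, SAEs are part of the primary endpoint and are likely to be few. With few events the choice of test matters, and with none in one arm a fitted rate ratio is zero or infinite. If the method is left open, software defaults may decide what is reported for the most important safety comparison.

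**Working it through.** **Inputs.** From 8.7: 20 per arm, alpha 5%, power 80%, effect 60%. Assumed because the documents do not say: two-sided testing, equal full follow-up, Poisson counts, and the placebo rates shown.

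**1. Where the 60% figure fits.** For a Wald test on the log IRR, the placebo mean per subject that gives 80% power is

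λ0 = (1.960 + 0.842)² × (1 + 1/IRR) / (20 × (ln IRR)²).

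- IRR 0.4: 7.849 × 3.5 / (20 × 0.8396) = 1.64
- IRR 1.6: 7.849 × 1.625 / (20 × 0.2209) = 2.89

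Full enumeration of Poisson outcomes with the exact conditional test gives 1.615 and 2.96. For a proportion under chi-square, a 60% relative reduction reaches 80% power at a placebo proportion near 73%. For a hazard ratio of 0.4, 4 × 7.849 / 0.8396 = 37.4 events are needed among 40 subjects. So the figure can be recovered for frequent events, but only by supplying a rate that the plan does not give.

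**2. Observed against true.** At 1.615 events per placebo subject, 20 × 1.615 = 32.3 placebo events are expected. Taking 33:

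- 18 v 33 events (18/33 = 0.545, 45% fewer): p = 0.049 exact, 0.034 likelihood ratio, 0.039 Wald.
- 19 v 33 events: p = 0.070 exact, 0.051 likelihood ratio.

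With a true IRR of 0.4 and 80% exact power, 50% of trials show a reduction above 60%. Of the significant trials, 35% show less than 60%.

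**3. Rare counts: an arm with no event.** With equal rates, P(at least one arm has none) = 1 − (1 − e^(−20λ))².

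- λ = 0.05: 1 − (1 − 0.368)² = 0.60
- λ = 0.10: 1 − (1 − 0.135)² = 0.25

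In those trials Poisson regression gives no finite, non-zero IRR and no usable Wald interval.

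**4. Rare counts: type I error by test** (enumeration; a Wald test with an empty arm is counted as not significant).

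| Events per subject | Likelihood ratio | Score | Exact | Wald |
|---|---|---|---|---|
| 0.05 | 6.0% | 1.4% | 0.04% | 0.0% |
| 0.1 | 9.7% | 4.1% | 0.5% | 0.06% |
| 0.2 | 7.8% | 4.5% | 1.8% | 1.1% |
| 0.5 | 5.4% | 5.2% | 2.9% | 4.1% |

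The 9.7% is about the peak for the likelihood-ratio test. As a single case, 3 v 0 events gives p = 0.041 by likelihood ratio, 2 × 0.5³ = 0.25 by exact test, and no Wald result.

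**5. Rare counts: power at 0.1 events per placebo subject.**

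| True IRR | Exact | Score | Likelihood ratio | Wald |
|---|---|---|---|---|
| 0.4 | 0.8% | 6.7% | 15.8% | 0.04% |
| 2.5 | 9.8% | 18.6% | 26.8% | 4.7% |

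Over 0.05 to 0.2 events per subject, the highest value for either IRR under any of these tests is 40%. For hospitalization by chi-square, a fall from 10% to 4% has 6.4% power (1.1% to 18.7% for a 60% reduction from placebo rates of 5% to 20%).

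**The case against.** The defence is strong on several counts, and most of it stands.

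- The 60% is an example and a floor, in a paragraph that concedes low power. A reader might infer that the figure is arithmetically wrong or that 40 subjects is the wrong number. The documents support neither: the figure fits frequent events, and a hypothesis-generating trial may be this size.
- No rule uses the 60%. The safety verdict in 8.4 is a count of related grade 4 or 5 SAEs in the belnacasan arm. Section 8.4 also sets no significance criterion for the Poisson comparison; it reports an IRR. The type I error figures therefore matter only if a p-value is reported. The missing interval and the empty-arm problem matter either way.
- The Poisson model is specified. Only the test, the interval and the empty-arm rule are open, and the dispersion fallback does not address an empty arm.
- A reader might extend the point to chi-square for hospitalization and death and call it invalid in small samples. With 20 per arm its type I error is at most 5.3%, so naming chi-square is not an error.
- An exact method is not the only reasonable choice. The score test has 4.1% type I error at 0.1 events per subject and more power to see harm.

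**Conclusion.** The point holds as a minor one, in two parts.

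1. Power is attached to the wrong quantity. Under two-sided 5% and the exact test, 80% power for a true 60% reduction needs about 1.6 events per placebo subject, and significance then starts near an observed 45% reduction. The sentence needs rewording and its assumptions; it does not apply to SAEs or hospitalization if they are as rare as assumed here.
2. For sparse counts the plan lacks a test, an interval and a rule for an empty arm. At 0.05 to 0.1 SAEs per subject, 60% to 25% of trials would be affected by an empty arm.

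The rates in part 2 are assumptions, because the documents give none. At 0.5 events per subject or more the choice of test matters much less. Overdispersion or dropout would lower power further. The absence of endpoint, direction and sidedness is mostly missing detail.

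**What to change.** **Section 8.7 and Synopsis.** Replace 'observed' with 'true' and state the assumptions, for example: *With 20 per arm, two-sided 5% and an exact test, 80% power requires a true AE count IRR of about 2.14 or 0.27 if placebo subjects average 1 event, 1.75 or 0.45 at 2, and 1.6 or 0.54 at 3; larger effects are needed under overdispersion. Comparisons of SAEs and hospitalization are not powered.* By enumeration, exact power at these six values is 79.6% to 80.5%.

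**Sections 8.4 and 8.5.** State that for sparse counts (for example, an arm with zero or very few events) the IRR is reported with an exact conditional confidence interval and test in place of the regression output. Keep Poisson or negative binomial regression for frequent AEs. The interval is informative about uncertainty: 2 v 2 events gives 0.07 to 13.8. With 3 v 0 events it still gives a lower limit: 0.025^(1/3) = 0.292, and 0.292/0.708 = 0.41, with no finite upper limit. Where follow-up differs, the conditional test should use each arm's share of total exposure instead of one half.

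**Cost.** A few sentences, with no added patients or visits. The exact method is conservative: about 0.5% type I error at 0.1 events per subject, and 9.8% power for an IRR of 2.5 against 18.6% for the score test. The score test is an acceptable alternative for the p-value if it is named in advance. The chi-square test for proportions can stay.
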